## 2. LIST OF ABBREVIATIONS

Abbreviation	Definition
ACR	American College of Rheumatology
CCP	Cyclic Citrullinated Peptide
CDAI	Clinical Disease Activity Index
DAS28	Disease Activity Score
DMARDs	Disease Modified Anti Rheumatic Drugs
ENCePP	European Network of Centres for pharmacoepidemiology and pharmacovigilance
EULAR	The European League Against Rheumatism
N/A	Non Applicable
NSAIDs	Non-Steroidal Anti-Inflammatory Drugs
RA	Rheumatoid Arthritis
RDW	Real World Data
RF	Rheumatoid Factor

**4. AMENDMENTS AND UPDATES**

None.

## 5. MILESTONES

Milestone	Planned date
Start of data collection	01 November 2018
End of data collection	01 December 2018
Final study report	01 February 2019

This protocol was written post the conduct and completion of analysis.

## 6. RATIONALE AND BACKGROUND

In the past 1–2 decades, treatment paradigms in rheumatoid arthritis (RA) have shifted dramatically from initial treatment with nonsteroidal anti-inflammatory drugs (NSAIDs), followed by cautiously progressive addition of disease-modifying antirheumatic drugs (DMARDs), to the current treatment approach of aggressive initiation of DMARD therapy soon after the diagnosis of RA has been made. This change in RA management results from increasing data supporting improved prognosis and outcomes with the initiation of DMARD therapy early in the course of symptomatic disease. Since the goals in RA management include not only disease remission, but also improved functional status, which is strongly associated with radiographic joint damage, an understanding of the impact that the initiation of appropriate treatment during early RA has on these outcomes is essential.

Accurate diagnosis of early RA begins with clear definitions of RA, as there is considerable variability in the literature regarding the time frame defining early RA. Previous intervention studies in early RA have included early RA as disease duration from 3 months to 3 years; however, with the knowledge of improved outcomes with earlier treatment in RA, it becomes clear that a shorter time interval for classification of early RA is clinically significant. Due to the wide range of definitions of early RA presented in the literature, it is difficult to characterize the specific time frame that defines early RA. However, it is now generally accepted that early RA is the onset of symptoms of joint (typically polyarticular) pain, stiffness, or swelling within the past 3 months, although in practical terms it may be difficult for rheumatologists to evaluate patients within that 3-month time frame, due to a variety of factors, including delay in referral of patients with early symptoms of inflammatory arthritis (IA) or delays in patients seeking medical attention for their symptoms.

Multiple studies have evaluated the benefits of early treatment of RA, including several that have evaluated the impact of early DMARD treatment on successful response to therapy. In particular, a meta-analysis of ~1,400 RA patients from 14 randomized controlled trials identified that one of the strongest predictors of response to therapy was a shorter disease duration at the time of treatment initiation.

## 7. RESEARCH QUESTION AND OBJECTIVES

The objective of this study is to see the impact of early initiation of etanercept on patient response compared to delayed introduction of biological treatment.

## 8. RESEARCH METHODS

### 8.1. Study Design

- **Retrospective analysis** of patients with RA that received etanercept from Baghdad teaching hospital (Rheumatology center) from 2012 until 2018 (inclusion and exclusion criteria will apply for selecting patients).
- **Primary aim:** determine the impact of early referral for management in patients with RA compared to delayed management.
- **Secondary aims:** Determine the influence of early referral on the response to biological treatment.

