#### Hypothesis

Our initial hypothesis is that there is no difference in response between early and delayed referral to biological treatment.

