### **8.3. Data Sources**

We identified patients in rheumatology registry with rheumatoid arthritis and obtained information on patient demographics (age, gender), education level (years), present smoking status, disease duration (years), current steroid therapy (yes/no), baseline DAS28 (Disease Activity Index 28) & CDAI (Clinical Disease Activity Index) RF (Rheumatoid factor) status, anticitrullinated protein antibody (anti-CCP) status. Primary Outcomes: Disease activity Index (DAS28) and CDAI in last follow up visit.

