### **8.6. Data Analysis**

Categorical covariates described by frequency distribution while continuous covariates expressed in terms of their mean and standard deviation or median and interquartile range as appropriate. Patients were divided according to the mean of disease duration groups (below and above mean) and unadjusted comparisons between groups of the covariates and the outcomes are evaluated using chi2 tests for categorical data, while for continuous data, we used the student's t-test for normally distributed variables and the Kruskall-Wallis test for non-parametric data.

We determined the effect of early referral on the biologic treatment response patients with RA a multivariate analysis by using a stepwise linear regression models. The response variable is defined as DAS28 and CDAI at last visit. The baseline variables considered demographic data, disease duration (years), methotrexate (yes/no), Current steroid therapy (yes/no), baseline DAS28 and CDAI, RF positive (yes/no), anti-CCP (yes/no), present smoking (yes/no).

We determined the effect of early response by using the difference between the base line DAS28 and CDAI. P value <0.05 considered statistically significant.

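### Referral is named as the exposure, but no listed variable measures it: disease duration stands in undeclared, in a cohort limited to patients kept on etanercept for at least 1 year

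*Combined protocol and SAP*

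**What the plan says.** The protocol states its question in five places.

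- **Section 7, objective:** the "impact of early initiation of etanercept on patient response compared to delayed introduction of biological treatment".
- **Section 8.1, primary aim:** to "determine the impact of early referral for management in patients with RA compared to delayed management".
- **Section 8.1, secondary aim:** "Determine the influence of early referral on the response to biological treatment".
- **Section 8.2, hypothesis:** that "there is no difference in response between early and delayed referral to biological treatment".
- **Section 8.6:** the stepwise linear regression is presented as showing what early referral does to the response to the biologic.

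The data listed in section 8.3 include, after age and gender, "education level (years), present smoking status, disease duration (years), current steroid therapy (yes/no"), then baseline DAS28 and CDAI, RF and anti-CCP. Section 8.6 adds methotrexate as a covariate. The groups are built from one of these variables: "Patients were divided according to the mean of disease duration groups (below and above mean").

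The registry described in section 8.2 covers patients on biologics. Section 8.1 takes those who received etanercept, and section 8.2.2 removes anyone with less than 1 year of use. Section 8.8 names missing data as the only limitation. Section 5 says that the protocol was written after the analysis was completed.

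**The concern.** Four of the five statements put the result down to referral, a step in care that comes before any biologic. The variable that forms the groups is something else. A difference by disease duration could arise because patients presented late, were referred late, spent long on conventional drugs, or waited for access to a biologic. Reporting it as an effect of referral credits one of these steps when none was measured separately.

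Because the analysis was already complete when the protocol was written, the stated question no longer shapes data collection. It governs how existing results are read. A reader planning referral services could take the study as evidence on referral, and section 8.8 would not warn against it.

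**Working it through.** There is no figure to reproduce: the plan states no sample size, effect size or standard deviation, and the point is whether the exposure is measured. The check sets the sections side by side.

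**Step 1. Which exposure is named.** Section 7 names the start of etanercept. The primary aim, the secondary aim, the hypothesis and the 8.6 sentence name referral. Referral: 4 of 5. No section defines referral or says what counts as early.

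**Step 2. What is listed.** Section 8.3 lists 10 baseline items: age, gender, education, smoking, disease duration, steroid use, DAS28, CDAI, RF and anti-CCP. Section 8.6 adds methotrexate, so 10 + 1 = 11. Items that give a referral date, a first-visit date or an interval to referral: 0. Items that describe the timing of disease or care: 1, disease duration. It is not declared to be a proxy for referral.

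**Step 3. What disease duration contains.** Assume that it runs from symptom onset to the start of etanercept; the protocol gives neither the origin nor the time of measurement. Then

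D = a + b + c,

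where a is the time from onset to seeking care, b the time from seeking care to referral, and c the time from referral to etanercept. Section 6 itself treats a and b as separate causes of late evaluation. Only D is recorded, so b cannot be recovered. A patient with small b and large c falls above the mean together with a patient with large b and small c. The first was referred early and the second late, yet the analysis treats them alike.

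If duration is instead counted from diagnosis, any delay before diagnosis drops out of D. Were diagnosis usually made after referral, D would then hold none of the referral delay. The missing definition therefore affects even how loosely D tracks referral.

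**Step 4. Who can be in the data.** Two selections take place after referral: reaching etanercept, and using it for at least 1 year. Patients referred early and managed without a biologic are absent. So are those who stopped etanercept within the year. If early referral changes the chance of either event, a comparison among those who remain does not give the effect of early referral for management. This holds however disease duration is cut, so it is separate from the choice of the mean as the dividing point.

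**Step 5. What the data can support.** Disease duration and DAS28 and CDAI at the last visit are all listed. Their association among etanercept-treated, biologic-naive patients can be estimated, and it corresponds to the section 7 objective once the origin and timing of disease duration are stated.

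**The case against.** The best reply is that referral is used loosely for the timing of treatment. The primary aim sets early referral against delayed management, not against late referral. The hypothesis speaks of referral to the biologic. The rationale in section 6 cites disease duration when treatment begins as a predictor of response. Read this way, disease duration is a recognisable proxy for the section 7 objective, and the defect is one of terms. This stands in part: it supports the section 7 question and, loosely, the hypothesis. It does not rescue a primary aim about referral for management, and the proxy is still undeclared.

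Three stronger readings are tempting, and the documents do not support them.

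- **A reader might infer that the study can answer nothing because every patient received etanercept.** Comparing early with late initiation needs no untreated group. The restriction matters for the referral aim because it conditions on events after referral.
- **A reader might infer that referral dates were never collected.** The lists show only that none is listed. Section 8.3 is visibly incomplete, since methotrexate appears in 8.6 but not there, and the registry may hold such a date.
- **A reader might infer that one model serves two identical aims.** The aims differ in wording, and section 8.6 also gives unadjusted group comparisons and an analysis of differences involving the baseline scores. None of these, however, brings in a listed measure of referral.

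It is also fair to say that the main remedy changes no computed estimate. It does change what the estimate may be said to show.

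**Conclusion.** The concern holds in this form: the listed data cannot identify the effect of early referral for management, while they can support an association of disease duration with later DAS28 and CDAI among patients who reached etanercept and stayed on it.

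In size, 4 of 5 statements of the question name an exposure that 0 of 11 listed baseline variables measure. The numerical error from reading the duration result as a referral effect cannot be calculated, nor can its direction, because the documents give no data on the separate delays or on the patients left out.

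The conclusion rests on two assumptions: that the lists in 8.3 and 8.6 cover every timing variable used in the analysis, and that no unstated definition equates disease duration with time to referral. An unlisted referral date would remove the measurement problem, but the selection on etanercept use would remain.

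**What to change.** 1. Reword the aims in 8.1, the hypothesis in 8.2 and the regression sentence in 8.6 to one question: the association of disease duration at etanercept start with DAS28 and CDAI at the last visit, in biologic-naive patients treated for at least 1 year.
2. State whether disease duration runs from symptom onset or from diagnosis, and when it was measured. If it was not measured at etanercept start, the new wording must say so.
3. Add to 8.8 that the results do not support a conclusion about referral and are conditional on reaching and staying on etanercept.
4. Record the rewording in section 4, which now lists no amendments, as made after the analysis was completed.
5. If the registry holds a referral or first-visit date, analyse it as a separate exposure, with the same caution about selection.

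Items 1 to 4 need text and one definition, and no new data. The price is a narrower claim and an open statement that the question was reworded once the analysis was done. Item 5 needs a further extraction and analysis, only if the date exists.

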### 8.2. Setting

#### Patients and Methods

Data collected from the Baghdad teaching hospital registry. The rheumatology patient registry is a prospective longitudinal multicenter cohort initiated in 2012. It captures all patients treated with biologic therapies managed in the rheumatology department. The decision to initiate and maintain the treatment is guided by the ACR (American College of Rheumatology) recommendations.

#### Study population

Patients included in the study if they met the American College of Rheumatology/EULAR (The European League Against Rheumatism) 2012 criteria for Rheumatoid Arthritis, with at least 1 year of follow up after starting their first biologic therapy.

Exclusion criteria: patients previously or currently treated with other biological therapies.

#### Hypothesis

Our initial hypothesis is that there is no difference in response between early and delayed referral to biological treatment.

#### 8.2.1. Inclusion Criteria

Patients must meet all of the following inclusion criteria to be eligible for inclusion in the study:

1. Diagnosed RA patients.
2. 18 years old and above.
3. Did not receive previous biological treatment.

### **8.2.2. Exclusion Criteria**

Patients meeting any of the following criteria will not be included in the study:

1. Had previous biological treatment.
2. Use etanercept for less than 1 year.

### **8.3. Data Sources**

We identified patients in rheumatology registry with rheumatoid arthritis and obtained information on patient demographics (age, gender), education level (years), present smoking status, disease duration (years), current steroid therapy (yes/no), baseline DAS28 (Disease Activity Index 28) & CDAI (Clinical Disease Activity Index) RF (Rheumatoid factor) status, anticitrullinated protein antibody (anti-CCP) status. Primary Outcomes: Disease activity Index (DAS28) and CDAI in last follow up visit.

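### Education level is collected but not named among the section 8.6 model variables, so on the document's own definition of demographics a plausible confounder goes unadjusted

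*Combined protocol and SAP*

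**What the plan says.** Section 8.3 (Data Sources) describes what was taken from the registry: "patient demographics (age, gender), education level (years), present smoking status, disease duration (years), current steroid therapy (yes/no", and then "baseline DAS28 (Disease Activity Index 28) & CDAI (Clinical Disease Activity Index) RF (Rheumatoid factor) status, anticitrullinated protein antibody (anti-CCP) status". The parenthesis after demographics is the only definition of that term in the document. Education follows as a separate item.

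Section 8.6 (Data Analysis) gives the variables for the adjusted models of DAS28 and CDAI at the last visit: "The baseline variables considered demographic data, disease duration (years), methotrexate (yes/no), Current steroid therapy (yes/no", continuing with "baseline DAS28 and CDAI, RF positive (yes/no), anti-CCP (yes/no), present smoking (yes/no". Demographic data is not itemised there. Education is not named; methotrexate is. The method is "a multivariate analysis by using a stepwise linear regression models".

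Section 5 (Milestones) adds that "This protocol was written post the conduct and completion of analysis". Section 8.8 names missing data as the one limitation and does not mention confounding.

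**The concern.** The study compares patients by disease duration, without randomisation. The regression in 8.6 is the only control of confounding that the plan describes, so a variable outside it is not adjusted for.

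Education is the only socio-economic variable collected. Section 6 gives "delays in patients seeking medical attention for their symptoms" as one reason why patients are not evaluated early, and education is a plausible driver of such delay. It may also relate to later disease activity through routes other than duration. If less-educated patients have longer disease at etanercept start and higher activity at the last visit for reasons unrelated to the delay, a model without education credits part of that difference to duration. The error would favour early start, which is the effect the study sets out to examine.

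**Working it through.** **Step 1. Compare the two lists.** Demographic data in 8.6 is read here as age and gender, following 8.3.

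| Item | Listed as obtained (8.3) | Model variable (8.6) |
|---|---|---|
| Age | yes | yes (demographic data) |
| Gender | yes | yes (demographic data) |
| Education level (years) | yes | **not named** |
| Present smoking | yes | yes |
| Disease duration | yes | yes |
| Current steroid therapy | yes | yes |
| Baseline DAS28 | yes | yes |
| Baseline CDAI | yes | yes |
| RF | yes | yes |
| Anti-CCP | yes | yes |
| Methotrexate | **not listed** | yes |

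Each list has 10 items and 9 match. Education stands only in 8.3 and methotrexate only in 8.6. If demographic data is read to include education, methotrexate is the only mismatch.

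**Step 2. What being listed would secure.** The 8.6 variables are candidates for a stepwise procedure, which may drop any of them. Adding education to the candidate list would therefore not ensure adjustment. It has to be held in the model.

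**Step 3. Illustrative size.** The plan gives no figure to reproduce and section 8.4 sets no study size. Every input below is an assumption except the 0.05 level, which is from 8.6 and is taken here as two-sided.

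- Correlation of education with duration, r: −0.15 to −0.35.
- Standardised effect of education on last-visit DAS28, β: −0.10 to −0.25.
- SD of last-visit DAS28: 1.4.
- N: 200 or 400.

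Bias in the duration coefficient, in SD of DAS28 per SD of duration, is b = r × β:

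- low: (−0.15) × (−0.10) = 0.015, and 0.015 × 1.4 = 0.02 DAS28 points;
- middle: (−0.25) × (−0.20) = 0.05, and 0.05 × 1.4 = 0.07;
- high: (−0.35) × (−0.25) = 0.0875, and 0.0875 × 1.4 = 0.12.

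The product is positive: longer duration appears to go with higher DAS28.

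With no true duration effect, the false-positive rate is P(Z > 1.96 − b√N) + P(Z < −1.96 − b√N). For b = 0.05 and N = 200, b√N = 0.707, so the rate is P(Z > 1.253) + P(Z < −2.667) = 0.105 + 0.004 = 10.9%.

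| b | N = 200 | N = 400 |
|---|---|---|
| 0.015 | 5.5% | 6.0% |
| 0.05 | 10.9% | 17.0% |
| 0.0875 | 23.6% | 41.7% |

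The formula assumes a fixed model and ignores overlap between education and the other covariates. It shows how the mechanism works and does not measure it here.

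**The case against.** **Education may already be in the model.** Section 8.6 leaves demographic data open, and many authors count years of education as demographic. This stands as a possibility, so the omission is the literal reading and not a certainty. But the only definition in the document excludes education, and on either reading the reader cannot tell whether it was adjusted for.

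**An imbalance would be visible.** Section 8.6 also compares covariates between the shorter- and longer-duration groups without adjustment. If education is among them, a difference would be reported. That would reveal possible confounding but not remove it.

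**Nothing in the documents shows that education confounds.** Correct. Section 6 mentions patient delay in the context of a three-month window and does not mention education, whereas the model uses duration in years. Plausible is the right word; likely would be too strong.

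**The figures may be too large.** Also fair. What matters is the association of education with duration and outcome after the other covariates. Baseline activity and smoking could carry much of it, so the upper rates may be overstated.

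**Methotrexate.** A reader might infer that it was never extracted, that the model therefore cannot be fitted, and that co-treatment differences go uncorrected. The documents do not support this. Section 8.3 does not claim to be complete, the protocol was written after the analysis, and 8.6 names methotrexate as a variable considered. An incomplete list in 8.3 is at least as likely as missing data. What remains is that it is not listed as extracted and that its timing is not given.

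**Conclusion.** The point holds for education. On the document's own definition of demographics, a variable already in hand and plausibly related to both disease duration and response is outside the only adjustment planned. Stepwise selection means that naming it as a candidate would not be enough. If education does confound in the direction described, the result is biased towards early start. Its size in this study is unknown. The range of 0.02 to 0.12 DAS28 points per SD of duration, and the error rates that go with it, depend wholly on the assumed correlations, SD and N. They should not be cited as this study's bias or type I error.

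For methotrexate the point is one of reconciliation only. The documents do not establish that it was missing from the data or from the fitted models.

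**What to change.** In 8.6, replace demographic data with an itemised list and include education level (years) as a fixed covariate, not subject to stepwise selection, in both the DAS28 and the CDAI last-visit models. If education was in fact already a candidate, say so and still hold it in the model.

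In 8.3 and 8.6, reconcile methotrexate: state whether it was recorded and at what time point, and add it to 8.3 if so. If it was not recorded, remove it from 8.6 and state that the estimate is not adjusted for it.

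The cost for education is one degree of freedom in each model and a rerun of an analysis already completed, plus the loss of any patients with missing education, whose number should be reported. Since 8.3 lists education as obtained, no new data collection should be needed. The methotrexate point needs only text if the variable is already in the data set.

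### DAS28 and CDAI are both primary at a per-test 0.05 with no rule for what counts as a difference in response, and a protocol written after the analysis cannot show a prespecified test

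*Combined protocol and SAP*

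**What the plan says.** - **One hypothesis.** The Hypothesis paragraph in section 8.2 reads: "Our initial hypothesis is that there is no difference in response between early and delayed referral to biological treatment". It does not say which score measures response.
- **Two primary measures.** Section 8.3 reads: "Primary Outcomes: Disease activity Index (DAS28) and CDAI in last follow up visit". Section 8.6 carries both into the model: "The response variable is defined as DAS28 and CDAI at last visit". Neither score is ranked above the other.
- **One threshold.** Section 8.6 reads: "P value <0.05 considered statistically significant". Sidedness is not stated, and there is no split, hierarchy or adjustment.
- **Several analyses of each score.** Section 8.6 compares two groups without adjustment ("Patients were divided according to the mean of disease duration groups (below and above mean"), fits stepwise linear regressions, and adds a further form: "We determined the effect of early response by using the difference between the base line DAS28 and CDAI". I read the last as change from baseline in each score, although the sentence is incomplete.
- **Timing.** Section 5 reads: "This protocol was written post the conduct and completion of analysis". Section 4 lists no amendments and Annex 1 lists no stand-alone documents, so the file shows no earlier plan.

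**The concern.** A hypothesis test needs a rule that turns results into a conclusion. Here one hypothesis is attached to two co-equal outcomes, and the rule is missing. If DAS28 gave p=0.03 and CDAI gave p=0.20, the plan would not say whether the hypothesis is rejected. A report that followed the plan to the letter could present the significant score as the primary result, and could do so whichever score it was.

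Normally a prespecified statement would settle this. Here the document postdates the analysis, so its labels cannot do that work. What is at stake is how much weight a reader may give to a significant primary outcome. The plan uses confirmatory language (primary aim, primary outcomes, a null hypothesis, a significance threshold), while section 8.8 names only missing data as a limitation.

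**Working it through.** **Inputs from the document.** Two primary outcomes (8.3, 8.6); threshold 0.05 (8.6); one hypothesis (8.2); protocol written after the analysis (5).

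**Assumptions.** Two-sided tests; test statistics Z1 (DAS28) and Z2 (CDAI) jointly normal with correlation r. The document gives no r, so a range is shown.

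**Step 1: the plan's own figure.** The plan states no sample size, power or familywise error rate. Its only figure is 0.05, which is the false-positive rate of one test taken alone.

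**Step 2: either score suffices.** With no effect on either score:

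P(at least one) = 1 − P(|Z1|<1.96 and |Z2|<1.96).

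At r = 0 this is 1 − 0.95² = 0.0975. For other values of r the bivariate normal probability is used.

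**Step 3: both scores required.** P(both) = 0.05 + 0.05 − P(at least one). At r = 0.8 this is 0.10 − 0.0781 = 0.0219.

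| r | Either suffices | Both required |
|---|---|---|
| 0 | 9.75% | 0.25% |
| 0.5 | 9.07% | 0.93% |
| 0.7 | 8.35% | 1.65% |
| 0.8 | 7.81% | 2.19% |
| 0.9 | 7.04% | 2.96% |
| 0.95 | 6.46% | 3.54% |

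The middle column is above 5% at every correlation below 1. The right-hand column can never exceed 5%, because both tests being significant is at most as likely as one given test being significant. The missing rule therefore decides which side of 5% the study falls on.

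**Step 4: more than one analysis per score.** As an illustration, suppose the last-visit value and the change from baseline are each tested for both scores, giving four tests. If independent, the chance of at least one false positive is 1 − 0.95⁴ = 18.5%. With assumed between-score correlation 0.6 to 0.9 and assumed baseline-to-last-visit correlation 0.3 to 0.5, simulation gives about 12% to 16%. This leaves out having both a group comparison and a regression for the same outcome. It also takes each test at its nominal level, which p-values after stepwise selection do not keep.

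**Step 5: timing.** Every rate above describes a rule fixed before the results were known. Section 5 excludes that for any rule written in this document or added to it now.

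**The case against.** The strongest reply is that 0.05 in section 8.6 is a per-test threshold. The plan promises no familywise rate, and section 8.6 speaks of the response variable in the singular, which fits a reading that needs both scores. This stands in part. A reader might infer that the 5% error rate has been broken outright. The document does not support that, because it nowhere says that one score is enough. What it supports is conditional: the rule is undefined, and under one of the two natural readings the rate exceeds 5%.

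Two other stronger readings are tempting and should be left aside:

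- A reader might infer from section 5 that the outcomes were chosen with the results in view. Section 5 dates the writing of the protocol, not the choice of outcomes. It shows only that prespecification cannot be demonstrated.
- A reader might argue that the two scores measure different things and so are likely to disagree. The document neither describes their components nor compares them. The point needs only a correlation below 1.

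It is also fair to say that the inflation from two scores alone is modest, that both measure disease activity and so are probably positively correlated, that this is a completed retrospective registry analysis, and that section 5 discloses its timing openly. These limit the size of the point but do not supply the missing rule. Nor does the document call itself exploratory.

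Finally, a both-required or Holm rule inserted now would itself be chosen with results available. That objection stands in full, and the fix does not rely on such a rule to control error.

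**Conclusion.** The concern holds in a conditional form. Two unranked primary outcomes serve one hypothesis at a per-test 0.05, with no statement of whether one or both must be significant. If either suffices, the false-positive rate for the two last-visit tests is 6.5% to 9.75% over correlations 0.95 to 0, an excess of about 1.5 to 4.75 percentage points. It is higher once the group comparison, regression and baseline-difference analyses are counted. If both are required, it stays at or below 5%. These figures rest on assumed two-sided tests, joint normality and an assumed correlation. The finding that the rate exceeds 5% when either suffices does not depend on which correlation below 1 is taken.

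Apart from any figure, the primary and initial-hypothesis labels cannot be shown to be prespecified, and no later rule can make them so. A significant result on one score should not be presented as a confirmatory test of the hypothesis.

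**What to change.** In sections 8.3 and 8.6 and in the study report:

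1. State that the outcomes and hypothesis were documented after the analysis, and that no multiplicity rule was prespecified.
2. Report DAS28 and CDAI with estimates and 95% confidence intervals for every analysis that was run, whatever the p-values.
3. Label the findings exploratory.
4. Describe a difference in response as consistent only if both scores agree in direction and both reach p<0.05 in one named analysis, and say that this rule is post hoc. It disciplines the description of results and does not restore an error rate. It also does not repair the p-values from stepwise selection.

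The cost is wording and some extra tabulation, with no new data. The downside is a less strong conclusion, since a significant result on one score alone could no longer carry the claim.
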